**Table 3: Ranges**

Value	Range
Height	90 - 250 cm
Weight	30 - 500 kg
BMI (automatically calculated)	15 - 40
Age	18 - 120 years
Catheter PV cryo ablation - Total no.	1 - 4
Catheter PV rf ablation - Total no.	1 - 4
Catheter PV 3D RF ablation - Total no.	1 - 4
Number of pharmalogical cardioversions	1 - 99 Total no.
Number of electrical cardioversions	1 - 99 Total no.
Number of admissions	1 - 9 Total no.
Number of drinks/day	5 - 99
AF burden (optional)	0 - 100 %
Documented LVEF	15 - 70 %
Documented anteroposterior left aterial diameter	0 - 100 mm
INR value	0,5 - 9

General time of the procedure	30 - 300 min
LSPV	0 - 40 no.
LIPV	0 - 40 no.
LCPV	0 - 40 no.
RSPV	0 - 40 no.
RIPV	0 - 40 no.
RMPV	0 - 40 no.
Other accesery vein	0 - 40 no.
Number of pharmalogical cardioversions	1 - 20 Total no.
Number of electrical cardioversions	1 - 20 Total no.
Documented LVEF	0 - 100 %
Number of pharmalogical cardioversions	1 - 99 Total no.
Number of electrical cardioversions	1 - 99 Total no.
AF burden	0 - 100 %

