## 7.3 Categorisations

Variable categorisations will be done and displayed for all variables created for subgroup definitions (number of patients treated with PVAC GOLD solely). Following variable categorisations will be also displayed:

- Age by categorisation 1 [years]: <65, 65-74, ≥75
- Age by categorisation 2 [years]: <65, 65-75, >75, 75-80, >80
- Weight [kg]: ≤60, >60
- Body Mass Index [kg/m^2]: <18.5, 18.5 to <25, 25 to <30, ≥30 (including WHO obesity classes I-III)
- Number of drinks/day > 10
- HAS-BLED: low, medium, high risk (defined at SAP chapter 7.4.2.1)
- CHA2DS2-VASc: low, medium, high risk (defined at SAP chapter 7.4.2.2)
- Previous ablation (none, 1, ≥ 2)
- Previous surgery for AF (none, 1, ≥ 2)
- Hospitalizations due to AF (none, 1, ≥ 2)
- INR before ablation (INR≤1, 0.85<INR<1.27, INR≥1)

All other categories will be determined based on the distribution of the respective baseline data. Additional categorisations can be added, if necessary.

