## 7.4 Transformation of Data

### 7.4.1 (Re-)Calculation of derived variables

Body Mass Index [kg/m^2]

ROUND (body weight [kg] / (body height [cm] / 100) ^2), .01)

Time to event

For the time to event analysis, the time until the occurrence of an event is presented in days [d] and calculated as follows:

Date of event occurrence – date of first documented procedure

Length of stay in rehabilitation [days]

ROUND((Date of discharge - Date of referral),1)

DAPT [dichotomous]

Dual antiplatelet therapy: Combination of Aspirin and an P2Y12 inhibitor (Clopidogrel, Prasugrel or Ticagrelor).

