### 7.5.2 Replacement of outliers

In general, outliers are evaluated as reported. In the event of highly implausible values (in the sense of extreme outliers) documented in the database after completion of data validation the following approach is used:

For some baseline variables (e.g. age, weight, height) as well as for vital signs so-called plausibility ranges will be defined (Table 3).

Observed values that are not within these ranges are set to missing within the analysis datasets. The intention of these ranges is to set them as wide as possible, so that only values that are obviously impossible (e.g. age of 150 years or systolic blood pressure of 20 mmHg) are set to missing. Borderline values confirmed by the investigator within a query will not be set to missing.

The definition of the ranges is always set in consultation with a medical expert. An appropriate documentation of the implausibility ranges is given in the following table of this SAP according to the ranges in the Data Validation Plan.

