## 8.8 Graphical analysis

Graphical analysis will be provided for final analysis. The graphs will be created using SAS. Predefined graphical analysis will be done for the following topics and strata. Additional graphical analyses can be carried out after database closure.

**Table 13:** Predefined graphical analysis

Target variable	Analysis method	Patients set or strata
Main objective:  AF re-occurrence by study definition during 12 months  Additional analysis: AF re-occurrence with and without considering the "blanking period" of 90 days  AF re-occurrence up to 14 month (end of FU period) after first documented procedure	Kaplan-Meier estimation (time-to-first-event)	
 
• BAS, FAS, EFAS
 
• AF type
 

Additional objective:  Phased RFA procedure safety	Kaplan-Meier estimation (time-to-first-event)	
 
• FAS
 
• Reason for ablation: index, repeated, re-ablation, left Afl
 

Anticoagulation medication before /during/ after/ at 12months FU	Graphical (stacked) bar analysis	
 
• FAS, EFAS
 
• LAAO implantation
 

Analysis of procedure time by 
 
• Site
 
• Operator
 
	Box-whisker plots	
 
• FAS, EFAS
 

Correlation between Anticoagulation and 
 
• INR
 
• ACT
 
• Stroke
 
	Suitable correlation methods	
 
• FAS
 

Correlation between AF re-occurrence and 
 
• BMI
 
• Age
 
	Suitable correlation methods	
 
• BAS, FAS, EFAS
 

COX regression analysis (SAP chapter 8.1.2)	Forest plot (for HR + CI)	
 
• FAS, EFAS
 

Analysis of DAP - by site	Box-whisker plots	
 
• BAS
 

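### The BMI plausibility range of 15 to 40 sets real high BMI values to missing by default, against the SAP's own aim of removing only impossible values

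*SAP*

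**What the plan says.** SAP section 7.5.2 (Replacement of outliers) starts from the position that outliers are analysed as reported. It then makes a special rule: "In the event of highly implausible values (in the sense of extreme outliers) documented in the database after completion of data validation" are handled through the ranges in Table 3. The rule reads: "Observed values that are not within these ranges are set to missing within the analysis datasets". Its purpose is stated next: "The intention of these ranges is to set them as wide as possible, so that only values that are obviously impossible" are removed, with an age of 150 years and a systolic pressure of 20 mmHg as examples. There is one exception: "Borderline values confirmed by the investigator within a query will not be set to missing".

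Table 3 gives these ranges:

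- height: 90 to 250 cm
- weight: 30 to 500 kg
- the row beginning "BMI (automatically calculated": 15 to 40

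Section 7.5.1 rules out replacing missing values, so a deleted BMI is not restored.

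BMI is used in several places. Section 7.4.1 derives it as "ROUND (body weight [kg] / (body height [cm] / 100) ^2), .01". Section 7.3 lists four BMI categories, the last being 30 and above, described as "including WHO obesity classes I-III". Appendix D compares the same four groups in the FAS and EFAS, among patients with BMI available. Table 13 in section 8.8 plans "Correlation between AF re-occurrence and" BMI, and also age, in the BAS, FAS and EFAS.

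**The concern.** The BMI range does not do what section 7.5.2 says the ranges are for. An upper limit of 40 does not separate impossible from possible values; it falls within the distribution of real patients. The registry sets no exclusion criteria, so that it reflects ordinary practice (protocol section 3.2), and such patients can be enrolled.

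The loss is one-sided at the top and depends on the value itself. By default the 30-and-above group loses its heaviest members, the BMI-recurrence correlation is computed on a truncated range, and the reported maximum, mean and upper percentiles of baseline BMI are pulled down. A reader of the report would see these patients counted as having no BMI, although their height and weight were recorded and retained.

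**Working it through.** The plan gives no figure to reproduce here. The check compares the BMI limits with what the SAP's own height and weight limits permit.

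**Inputs.** Height 90 to 250 cm, weight 30 to 500 kg and BMI 15 to 40 (SAP Table 3); BMI formula (SAP section 7.4.1); planned size 800 to 1000 (SAP section 3.3).

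**1. BMI permitted by the height and weight ranges.** BMI = weight / (height / 100)².

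- Lowest: 30 / 2.50² = 30 / 6.25 = 4.80
- Highest: 500 / 0.90² = 500 / 0.81 = 617.28

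The component ranges admit 4.8 to 617. The BMI row is far tighter and is the row that does the deleting.

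**2. Weight at which BMI reaches 40.** Weight = 40 × (height / 100)².

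| Height (cm) | Weight at BMI 40 (kg) |
|---|---|
| 160 | 102.4 |
| 170 | 115.6 |
| 175 | 122.5 |
| 180 | 129.6 |

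All four weights lie in the lower part of the 30 to 500 kg range that the SAP treats as plausible.

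**3. Two example patients.**

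- 175 cm, 130 kg: 130 / 1.75² = 130 / 3.0625 = 42.45
- 180 cm, 150 kg: 150 / 1.80² = 150 / 3.24 = 46.30

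In both, height and weight are in range and kept, but BMI is out of range and set to missing by default. The first might be argued to be borderline; the second is not plainly so.

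**4. Number affected.** The documents give no proportion with BMI above 40. Assuming 1 to 4%:

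- 800 patients: 0.01 × 800 = 8 to 0.04 × 800 = 32
- 1000 patients: 0.01 × 1000 = 10 to 0.04 × 1000 = 40

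The overall span is 8 to 40, before any value is rescued by the query exception. These counts are scaled to the planned size; the FAS and EFAS will be smaller than the number enrolled, and the counts shrink in proportion.

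**The case against.** Four arguments can be made for the SAP as written.

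**The rule is narrow and has an exception.** It is aimed at extreme outliers left after validation, and confirmed borderline values are kept. An investigator could confirm a calculated BMI by confirming the height and weight behind it. This has some force: the loss is a default, not a certainty. It does not remove the problem. Table 3 is the only working definition of implausible in the section, and it classes a BMI of 41 as implausible. Borderline is undefined, nothing says that a BMI above 40 triggers a query, and the Data Validation Plan that might say so is not among the documents.

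**The range may apply only to the eCRF field.** Section 7.4.1 recalculates BMI, so the analysis variable might escape the range. The SAP does not say this. Table 3 names the calculated BMI, and nothing exempts the re-derived one. If the range is not meant to apply to it, the row needs editing for that reason.

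**No separate class III row is shown.** A reader might infer that the SAP plans a class III row which is empty by construction. The documents do not support that. The words in section 7.3 may mean only that the 30-and-above category pools classes I to III, and Appendix D has just four groups. The SAP gives no class cut-offs. Even if class III is taken as 40 and above (an assumption), a BMI of exactly 40 may be in range, and confirmed borderline values are kept.

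**The analyses are exploratory.** This is true and limits the weight of the point.

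A reader might also see the same fault in LVEF, which Table 3 lists once as 15 to 70% and again as 0 to 100%. The second row follows the procedure items and probably belongs to a different form, so the two ranges do not by themselves show an error.

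**Conclusion.** The point holds as a conflict inside the SAP. The BMI range of 15 to 40 is inconsistent with the stated aim of section 7.5.2, with the height and weight ranges in the same table, and with a top BMI category described as covering all obesity classes. By default it removes real values from the upper tail of the Appendix D comparison and the Table 13 correlation.

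The size is modest. Only the BMI value is lost; the patient still counts in the overall main-objective and safety estimates, and the 30-and-above group remains populated. The figure of 8 to 40 patients rests wholly on the assumed 1 to 4% and on no value being rescued by query. How far the correlation would change cannot be worked out, because the SAP says only that suitable methods will be used. That the class III category is wiped out, or that the loss is certain for every patient above 40, goes further than the documents allow.

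**What to change.** Change the BMI row of Table 3 in one of two ways:

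1. Widen the range so that it removes only impossible values, as section 7.5.2 intends.
2. Use the range only as a query trigger, and keep any BMI whose height and weight are both in range and verified.

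Verification matters in the second option. Keeping every BMI computed from in-range height and weight without a check would admit anything from 4.8 to 617, including values that point to an entry error.

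In either case, state that the rule applies to the BMI re-derived under section 7.4.1, and make the matching change in the Data Validation Plan, because section 7.5.2 ties the Table 3 ranges to it.

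The cost is one table row, one sentence and the aligned entry in the Data Validation Plan. No new data are needed, since height and weight are already collected. The downside is a few more queries and a slightly higher chance of keeping an entry error.

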Current AF treatment strategies include antiarrhythmic drug therapy, catheter based ablation, oral anticoagulation therapy to mitigate thromboembolic events, and therapy for concomitant diseases. However, antiarrhythmic drug therapy is often unsuccessful due to intolerance and/or ineffective treatment of AF and can increase the incidence of arrhythmia. Catheter ablation has shown to be a safe and effective treatment strategy for AF and therefore it has become an established invasive strategy for drug refractory AF. Approximately 50,000 ablations are performed annually in the US, and about 60,000 in Europe (6), and favorable outcomes suggest that this approach will remain a popular alternative to chronic drug therapy. Catheter ablation treatment strategies for AF have evolved over time and currently include isolation of the pulmonary veins (PVI) as the cornerstone of therapy. For patients with paroxysmal AF (PAF) PVI has been shown to be an effective treatment (7).

PVI has also been shown to be effective in patients with persistent and long-standing persistent AF (8).

However, for some patients with persistent/longstanding persistent AF, antral PVI alone may be insufficient as the location of drivers expands beyond the PVs into other areas of the left atrium and septum. In addition to PVI, linear and focal ablation strategies have demonstrated improved long-term outcomes (9). However, recent results from the STAR AF study have suggested, that additional linear or focal lesions may not improve efficacy compared to PVI alone (10). Overall, there is no consensus on the optimal ablation substrate for patients with persistent AF (11) and therefore different ablation strategies are utilized in various electrophysiology (EP) laboratories worldwide (12).

Historically, conventional point-by-point RF (hereto referred to as conventional) ablation procedures have often required advanced mapping and navigation tools (3-dimensional electro-anatomical mapping), tend to be long (4-6 hours) and need large numbers of ablations to achieve the desired therapeutic endpoint.

Recognizing the need for catheter improvement to shorten procedural times and potentially increase efficacy via contiguous lesions led to the development of the Medtronic Phased RFA system (Ablation Frontiers, Medtronic, U.S.) (13, 14).

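### The 30–300 minute plausibility limit on procedure time can set valid long procedures to missing, against the SAP's own stated purpose for such limits

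*SAP*

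**What the plan says.** SAP 7.5.2 starts from a sound default: "In general, outliers are evaluated as reported". For highly implausible values that remain after data validation it adds a deletion rule: "Observed values that are not within these ranges are set to missing within the analysis datasets". It states the purpose: "The intention of these ranges is to set them as wide as possible, so that only values that are obviously impossible" are removed, with an age of 150 years and a systolic pressure of 20 mmHg as examples. It allows one exception: "Borderline values confirmed by the investigator within a query will not be set to missing". The term borderline is not defined.

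On scope, the section says: "For some baseline variables (e.g. age, weight, height) as well as for vital signs so-called plausibility ranges will be defined". Procedure time is neither a baseline variable nor a vital sign. Table 3 nevertheless lists "General time of the procedure" with a range of 30–300 minutes.

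SAP 8.3.2, Table 10, uses that field (F20000611) as procedure duration, the first of five efficiency parameters. SAP 8.8, Table 13, plans box plots of procedure time by site and by operator. SAP 7.5.1 does not replace missing values.

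The protocol's Introduction says that conventional point-by-point procedures historically "tend to be long (4-6 hours".

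**The concern.** A limit that deletes data should lie where no real value can occur. This upper limit lies inside a duration that the protocol itself reports for AF ablation, so the number in Table 3 does not serve the purpose stated in 7.5.2.

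Long cases are foreseeable here. Protocol 4.4.3 describes persistent AF ablation as challenging and long. It also expects 3D systems and irrigated catheters at centres without a steerable sheath. SAP 8.3.2 reports efficiency for additional procedures, training cases, and cases with other catheters or adjunctive devices. These are the procedures most likely to pass 300 minutes.

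The protocol's rationale for the efficiency objective is that the technology shortens procedures. Loss of valid values from the upper tail would flatter that result. It would also affect the comparison of sites and operators, because a site with more complex cases would lose more of its values.

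**Working it through.** **1. Units.** The protocol's 4–6 hours is 4 × 60 = 240 to 6 × 60 = 360 minutes. The limit of 300 minutes is 5.0 hours, the midpoint. The part of that interval outside the range is (360 − 300)/(360 − 240) = 0.5. Half of an interval given as typical for one ablation technique cannot be obviously impossible.

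**2. What happens to a long value under the SAP.**
- A recorded time of 350 minutes with an unanswered query is set to missing.
- A time of 350 minutes confirmed by the investigator has no clear status, because it is not said whether 350 is borderline.
- A confirmed time just above 300 is presumably kept.

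**3. Possible size.** The documents give no distribution of Phased RFA procedure times, so these figures rest on assumption. Take times as lognormal with median M and log-SD s, and let a = (ln 30 − ln M)/s and b = (ln 300 − ln M)/s.
- Share above 300 = 1 − Φ(b); share below 30 = Φ(a).
- Full mean = M·exp(s²/2).
- Mean after both cuts = full mean × [Φ(b − s) − Φ(a − s)] / [Φ(b) − Φ(a)].

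Example with M = 100 and s = 0.5: a = −2.408, b = 2.197, full mean 113.3. Mean after both cuts = 113.3 × (0.9552 − 0.0018)/(0.9860 − 0.0080) = 110.5, lower by 2.9 before rounding.

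| Assumed median (min) | Log-SD | Above 300 | Below 30 | Fall in mean (min) |
|---|---|---|---|---|
| 100 | 0.3 | 0.01% | 0.00% | 0.0 |
| 100 | 0.4 | 0.30% | 0.13% | 0.6 |
| 100 | 0.5 | 1.40% | 0.80% | 2.9 |
| 150 | 0.3 | 1.04% | 0.00% | 1.9 |
| 150 | 0.5 | 8.28% | 0.06% | 19.4 |
| 180 | 0.3 | 4.43% | 0.00% | 7.1 |
| 180 | 0.5 | 15.35% | 0.02% | 35.5 |

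The table treats every value outside the range as deleted. Confirmed values that are kept would make the falls smaller.

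**4. The two cuts act in opposite directions.** In the worked example the upper cut alone gives 113.3 × 0.9552/0.9860 = 109.8, a fall of 3.5 minutes. Adding the lower cut brings the mean back to 110.5.

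**5. Median and quartiles.** In the same example the retained share is 1 − 0.0140 − 0.0080 = 0.978. The reported median is then the original percentile 0.008 + 0.5 × 0.978 = 0.497, and the reported upper quartile is 0.008 + 0.75 × 0.978 = 0.742. Both barely move. With M = 180 and s = 0.5 the reported median would be the original percentile 0.0002 + 0.5 × 0.8463 = 0.423, so this reassurance fails if many values are removed.

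**The case against.** The strongest reply is that the SAP already queries before it deletes. Outliers are by default analysed as reported, the rule applies only after data validation, and confirmed borderline values stay. The protocol plans range checks (section 7) and queries to the investigator (7.1.2). SAP 8 reports the number of missing values for continuous data, and Appendix D lists an analysis of missing data. Much of this stands. What remains open is that borderline is undefined, that an unanswered query still ends in deletion, and that a general missing count does not show how many values this rule removed.

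Three stronger readings are tempting, and the documents do not support them:
- **That the reported maximum cannot exceed 300 minutes.** A confirmed value above 300 can survive under the exception.
- **That long cases vanish from the efficiency results.** Only the eCRF-calculated time is limited. Laboratory occupancy and fluoroscopy time have no range in Table 3. Nor does the SAP 7.4.1 interval from first vessel access to last catheter removal, which matches the protocol's definition of total procedure time.
- **That the bias runs wholly in favour of the device.** The 30-minute cut raises the mean. It concerns a narrow group, because SAP 8.3.2 already leaves out procedures without RF applications.

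It is also fair that 4–6 hours describes historical conventional ablation and not Phased RFA, which the protocol presents as quicker. The comparison cut of 100 minutes in Appendix D suggests typical times well below 300. The overlap shows that such times are possible, not that they are common here. Finally, the wording of 7.5.2 names baseline variables and vital signs, so the rule reaches procedure time only through the Table 3 entry.

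**Conclusion.** The concern holds in a limited form. The 300-minute limit conflicts with the intent stated in SAP 7.5.2, and the rule as written can remove valid long procedure times. The result would be a lower mean, SD, 95th percentile and maximum for procedure duration, and altered plots by site and operator.

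The size cannot be determined from the documents. Under the assumed lognormal distributions the mean falls by about 0–3 minutes at a median of 100. Larger falls, up to about 36 minutes, need medians of 150–180 minutes and a wide spread, for which the documents give no support.

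Only one of the five efficiency parameters is affected, the objective is ancillary, and the analysis is descriptive. Severity is minor to moderate. The change is worth making because a stated rule can delete correct data and is cheap to repair.

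**What to change.** Amend SAP 7.5.2 and Table 3 for procedure time:
- Use 30–300 minutes only as a query trigger.
- Keep every investigator-confirmed value, whether or not it would count as borderline.
- Set a time to missing only if the site confirms an error or the recorded clock times contradict it.
- Report the number of procedure times set to missing by this rule, separately from times never recorded.
- State that the rule covers procedural variables listed in Table 3, so that the text and the table agree.

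The cost is a change of SAP wording and a few extra queries.

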## 7.6 Self-Evident Corrections

Self-evident corrections will not be implemented in the raw data but on basis of the analysis data sets. They are described in the Data Validation Plan.

# 8 Descriptive Statistics

This section describes the most relevant parts of the statistical analyses planned for this registry. All planned statistical methods will be described in detail in the Statistical Analysis Plan, which should be finalized prior to interim analysis and need to be finalized prior final analysis.

In general, this registry is intended to collect data under real life conditions. The statistical analysis will be performed in explorative and descriptive manner, i.e. no pre-specified hypothesis testing.

All variables collected in the CRF as well as the data obtained from the QoL assessments and all derived parameters will be used in the statistical analysis.

Binary, categorical, and ordinal parameters will be summarized by means of absolute and percentage numbers within the various categories.

Continuous data will be summarized by means of standard statistics, i.e. number of available data, number of missing data, mean, standard deviation, minimum, median, maximum, 5th and 95th percentile, lower and upper quartile (see SAP Appendix A).

Time-to-event data is planned to be analysed via a Cox proportional hazard regression model presenting hazard ratios and the corresponding 95% CI. In addition, Kaplan-Meier

curves may be presented for the time-to-event data. Two-sided 95%-CI will be presented for important parameters, but should be interpreted in an exploratory descriptive way. No formal statistical tests are planned within the statistical analysis. Event rates will be calculated for 3, 6, 9 and 12 months after first documented procedure and may be displayed graphically.

To measure statistical differences in continuous or dichotomous/ multinomial variables between baseline and 12 month FU non-parametric (e.g. Friedman's Chi-Square Test, McNemar's Test) will be utilized. The test is only performed if the variable is not missing at admission and discharge.

A biometrical report including descriptive statistics of all relevant documented parameters will be generated for the overall patient population as well as for each participating country (SAP chapter 8.7). Depending on the variable(s) of interest, additional selection criteria for subjects (e.g. subgroup analyses) considered in specific analyses may be used, if considered useful during the statistical analysis (SAP chapter 8.6).

Any change to the data analysis methods described in the CIP will require an amendment only if it changes main and additional objectives of the CIP. Any other changes to the data analysis methods described in the CIP, and the justification for making the change, will be described in the clinical study report.

In order to assess the effects of patients lost to follow-up, percentages of dropouts and reason for loss to follow-up will be summarized. In addition, baseline characteristics of patients who were lost to follow-up in comparison to patients with a complete follow-up will be described.

Additionally, adequate graphs (e.g. bar charts, box-whisker plots) may be presented to summarize the results for some parameters. Further descriptive statistical analyses will be carried out, e.g. correlation analysis (SAP chapter 8.8).

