- Treated with the PVAC GOLD catheter only in persistent AF patients

Evaluate QoL (AFEQT) dynamic through 12 months.

Rational: Symptom relief and improvement in QoL are the major therapeutic goals of PVI. The validated AFEQT questionnaire designed specifically to assess the impact of AF burden on patient's QoL. Improvement in QoL will be used as a subjective indicator of Phased RFA long term success.

Endpoint definition: AFEQT questionnaire completed at baseline and at 12 months FU.

Analysis Methods: Change in QoL from baseline to 12 months will be summarized using mean, SD, minimum, median, maximum and IQR. Statistically significant change from baseline will be assessed using a two-sided t-test.

Limitations: If QoL was completed at baseline, but missed for 12 months FU, this patient will be excluded from the analysis. As far as QoL is not a standard of care in some hospitals it is up to patient consideration to complete or to refuse QoL completing.

5 Project Termination

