### 8.3.5 Evaluate QoL (AFEQT) dynamic at 12 month FU

Quality of Life analysis will be done for all available subjects. Therefore, completed AFEQT questionnaire at baseline and at 12 month FU will be used. With it, single scales and AFEQT score will be analysed at baseline and at 12 months. Also, absolute and relative differences in AFEQT score between baseline and 12 months will be displayed. Score calculations are described in SAP chapter 7.4.3, rules for analysis in SAP chapter 6.3.

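### The SAP's condition for its baseline-to-12-month tests names the wrong time points, and the protocol's t-test for AFEQT change is dropped without explanation, leaving Friedman's test as the example for continuous data

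*SAP*

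**What the plan says.** **Protocol, section 4.4.3 (QoL objective).** The endpoint is "AFEQT questionnaire completed at baseline and at 12 months FU". For the analysis, "Statistically significant change from baseline will be assessed using a two-sided t-test". Patients with a baseline score but no 12-month score are left out.

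**SAP, section 8.** The comparison is introduced with "To measure statistical differences in continuous or dichotomous/ multinomial variables between baseline and 12 month FU", and the method is "between baseline and 12 month FU non-parametric (e.g. Friedman's Chi-Square Test, McNemar's Test) will be utilized". The sentence that follows is "The test is only performed if the variable is not missing at admission and discharge". The paragraph before it states: "No formal statistical tests are planned within the statistical analysis".

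**SAP, Table 2 (section 7.1).** The pre-post pairs are baseline to 12-month follow-up for AFEQT, AF burden and EHRA class, and discharge to 12-month follow-up for medication.

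**SAP, section 8.3.5.** For AFEQT, "completed AFEQT questionnaire at baseline and at 12 month FU will be used". Absolute and relative differences are displayed. No test is named. Section 8.3 sends ancillary objectives to the chapter 8 methods unless something else is described.

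**The concern.** Two adjacent sentences in SAP section 8 name different time points: one compares baseline with 12 months, and the next lets the test run only where admission and discharge values exist. A programmer who follows the second sentence would run no test for AFEQT. For medication, the programmer would select patients by the wrong criterion.

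The choice of test is also open. The protocol names a t-test on the AFEQT change. The SAP offers non-parametric examples instead, and also says that no formal tests are planned. Three instructions that do not agree leave the method to be chosen once the data are visible. The protocol treats QoL improvement as a subjective indicator of long-term success, so its analysis should be fixed beforehand.

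**Working it through.** The documents give no SD, effect size or power for the AFEQT change, so there is no stated figure to reproduce.

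**1. Time points side by side**

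| Variable | Pair in SAP Table 2 | Effect of requiring admission and discharge values |
|---|---|---|
| AFEQT | baseline, 12 months | cannot be met: the flow charts (protocol Table 7-1, SAP 3.2) show AFEQT only at baseline and 12 months |
| AF burden, EHRA class | baseline, 12 months | discharge is not an end of the pair |
| Medication | discharge, 12 months | can be met, but does not require the 12-month value |

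The condition fits no pair in the table.

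**2. Which rule governs AFEQT.** SAP 8.3.5 names no test, so SAP 8.3 points back to chapter 8. Protocol 4.4 says that changes in analysis method, with their justification, are to be described in the SAP. SAP section 8 moves that description to the clinical study report. The SAP gives no reason for dropping the t-test.

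**3. Friedman's test with two time points.** Let n be the number of pairs, n₊ and n₋ the numbers of rises and falls, and D = n₊ − n₋. The rank sums are R₁ = 3n/2 − D/2 and R₂ = 3n/2 + D/2. With k = 2:

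- Uncorrected statistic: 12/(n·2·3) × (R₁² + R₂²) − 3n·3 = (2/n)(9n²/2 + D²/2) − 9n = D²/n.
- Tie correction: divide by (n₊ + n₋)/n.
- Result: D²/(n₊ + n₋), the sign-test statistic.

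On three simulated sets of 300 pairs with ties, both formulas gave 13.337, 6.785 and 14.148. The size of each change is ignored.

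**4. Efficiency.** The asymptotic efficiency of the sign test against the paired t-test is 4σ²f(0)², where f is the density of the differences. For normal differences f(0) = 1/(σ√(2π)), which gives 2/π = 0.637. Against the Wilcoxon signed-rank test it is 2/3 = 0.667. Efficiency against the t-test for other shapes: uniform 0.33, logistic 0.82, t with 5 df 0.96, t with 3 df 1.62, Laplace 2.0.

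**5. Power.** Assumptions: normal differences, two-sided 5% level, true change of d SDs.

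- Paired t-test (normal approximation): Φ(d√n − 1.96).
- Sign test: with p = Φ(d), Φ{[(p − 0.5)√n − 1.96 × 0.5] / √(p(1 − p))}.
- Example, n = 800 and d = 0.1. t-test: Φ(2.828 − 1.96) = 0.807. Sign test: p = 0.5398, and Φ[(0.0398 × 28.28 − 0.98)/0.498] = 0.616.

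| Pairs | 0.1 SD: t / sign | 0.2 SD: t / sign | Change detectable with 80% power (SD): t / sign |
|---|---|---|---|
| 400 | 52% / 36% | 98% / 89% | 0.140 / 0.176 |
| 600 | 69% / 50% | 99.8% / 97% | 0.114 / 0.144 |
| 800 | 81% / 62% | 99.99% / 99.5% | 0.099 / 0.124 |
| 1000 | 89% / 71% | about 100% / 99.9% | 0.089 / 0.111 |

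The 800 is the evaluable number that SAP 3.3 plans for re-ablation prevalence. It is not a forecast of AFEQT pairs. QoL completion is optional (protocol 4.4.3), and SAP 6.3.1 may exclude or split AFEQT data, so some tests may have fewer pairs.

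**The case against.** The strongest reply is that this is one wrong word in a descriptive registry. The SAP elsewhere uses admission for baseline (the first-visit heading in Appendix B, the EHRA row in Appendix D), and the sentence before the condition fixes the intended pair. SAP Table 2 and section 8.3.5 do the same for AFEQT. QoL is ancillary, no decision rests on the p-value, and with 800 pairs either test detects a change of 0.2 SD. All of this stands, and it limits the consequence. It does not remove the contradiction or explain why the protocol's test was dropped.

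A reader might infer more than the documents support:

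- **That the test is either never run or loses a third of its information.** Never run requires a literal reading of what is probably leftover text. Friedman's test is given only as an example, so a Wilcoxon signed-rank test is allowed. A loss of about a third assumes normal changes, and for heavy-tailed changes the sign test can be the better one.
- **That no effect size is reported.** SAP Table 2 and section 8.3.5 both provide for the AFEQT change, and section 8 plans 95% CIs for important parameters.
- **That baseline and 12-month scores come from conflicting populations**, because of "Quality of Life analysis will be done for all available subjects". The next sentence of 8.3.5 uses questionnaires completed at both times. Without imputation, a change exists only in patients who have both scores.
- **That McNemar's test is assigned to multinomial variables.** SAP section 8 lists variable types and then example tests, without matching them.

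**Conclusion.** The point holds as an error of wording and an unreconciled difference between protocol and SAP. The admission-and-discharge condition contradicts the sentence before it, fits no pair in SAP Table 2, and read literally cannot be met for AFEQT. The protocol's t-test for AFEQT change is not carried forward and no reason is given, while the SAP both suggests tests and says that none are planned.

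If Friedman's test were used for AFEQT, the loss would be about 36% in efficiency against the paired t-test (1 − 0.637). In power at 800 pairs, that is about 19 percentage points at 0.1 SD and almost nothing at 0.2 SD. These figures assume roughly normal changes and a two-sided 5% level, and the documents give no distribution for AFEQT change. The main objective is unaffected. The correction is worth making because it costs almost nothing and removes a choice that could otherwise be made after seeing the data.

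**What to change.** Amend SAP sections 8 and 8.3.5:

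- Replace the condition with: not missing at baseline and at the 12-month follow-up. For medication, require values at discharge and at the 12-month follow-up, as in SAP Table 2.
- For AFEQT, report the mean paired change with its 95% CI and the protocol's two-sided t-test on the paired change, with the Wilcoxon signed-rank test as a sensitivity check. Remove Friedman's test for comparisons of two time points. If the sponsor prefers a non-parametric main test, state the reason in the SAP.
- Keep McNemar's test for two-level variables. For EHRA class, name a paired method that uses the ordering of the categories.
- Label all these tests exploratory, and reword the statement that no formal tests are planned so that the two agree.

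The cost is SAP wording and the matching table specifications. No new data are needed, and the protocol's AFEQT method can stay as it is.
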